3.0 Objectives/Aims

Our aim is to test the **central hypothesis** is that perimenstrual E2+P4 withdrawal induces rapid withdrawal from calming GABAergic neuroactive steroids, which in turn increases hyperarousal and hopelessness, which then interact to cause proximal suicide risk (Figure 1). P4 is metabolized to GABAergic neuroactive steroids, and E2 promotes expression of enzymes that convert P4 to neuroactive steroids⁹³. Perimenstrual E2+P4 withdrawal may increase suicide risk by causing rapid withdrawal from the antidepressant⁹ and sedative^{11,10} effects of neuroactive steroids⁹⁴, as well as withdrawal from the antidepressant effects of E2⁹⁵. Our preliminary experimental work strongly suggests that perimenstrual E2+P4 withdrawal (and neuroactive steroid withdrawal) heightens proximal suicide risk via hopelessness⁶⁵ and hyperarousal^{12,66}.

Figure 1. Peri-menstrual Hormone Withdrawal and Proximal Suicide Risk

Design: Using the PI’s hormone withdrawal paradigm (K99MH109667¹²), a new sample of 90 completers female outpatients with past-month SI will complete two counterbalanced conditions: (1) natural perimenstrual E2+P4 withdrawal (placebo), and (2) perimenstrual E2+P4 stabilization. Five labs per condition will capture changes in neuroactive steroids, mRNA expression for neurosteroidogenic enzymes, physiological arousal, behavioral indices of arousal, and interview/self-report indices of proximal suicide risk, hopelessness, and hyperarousal. Our app (BiAffect) will passively track indices of arousal including psychomotor agitation (accelerometer) and reactivity (typing speed variability). Additionally, Metricwire will passively track movement using smartphone sensors. 40 healthy controls (HC) will complete five labs across one observational cycle to characterize 1) normative cycle-related variation in neuroactive steroids and mRNA expression, and 2) group-related differences (i.e., past-month SI vs HC) in trajectories of GABAAR subunit change across the cycle.

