4.0 Eligibility

Recruitment and Screening. We will recruit **170 females (90 completers) with past-month SI** in outpatient treatment as usual with a mental health provider, and 60 healthy controls (HC) (40 completers) with no lifetime history of SI and no DSM-5 diagnoses in the past five years, for a total of 230 participants. Participants will be recruited via fliers, email listservs, online Research “match” websites (Research Match, Research & Me), and social media ads seeking volunteers to participate in a study “on the biology of depression, stress, and suicide” (with no mention of the cycle, hormones, female sex, or women). Participants will complete an online screener and will be scheduled for a phone screen if they meet basic inclusion criteria. Following phone screening, potential participants will be invited to an enrollment visit.

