6.0 Study Design and Procedures

Overview of Research Design. The proposed primary experiment (identical to K99MH109667) tests the hypothesis that perimenstrual E2+P4 withdrawal causes varying degrees of neuroactive steroid withdrawal, which produces co-occurring hopelessness and hyperarousal, which interact to cause proximal suicide risk. In a crossover placebo-controlled experiment, 90 completer female outpatients with recent SI (but acceptable suicide risk for outpatient treatment) will complete two counterbalanced perimenstrual conditions: (1) natural perimenstrual hormone withdrawal (placebo), and (2) prevention of perimenstrual hormone withdrawal (exogenous stabilization of E2+P4). Measures of neuroactive steroids, hopelessness, hyperarousal, and proximal suicide risk will be collected in the laboratory and via smartphone. The basic timeline for participation can be seen in Table 1a. We will utilize scientifically rigorous methods that promote transparency and reproducibility (NOT-OD-16-012): well-defined inclusion/exclusion criteria, validated measures, pre-registration of our protocol, and sharing of data.

Table 1a. Primary study activities and timeline.

STUDY TIMELINE	START	MONTH 1		MONTH 2				MONTH 3	MONTH 4				END	
	Enrollment Visit	Welcome Visit	Baseline Menstrual Cycle	STUDY PHASE 1 MENSTRUAL CYCLE				WASHOUT MENSTRUAL CYCLE	STUDY PHASE 2 MENSTRUAL CYCLE					
				Week 1	Week 2	Week 3	Week 4		Week 1	Week 2	Week 3	Week 4		
Order A (Half of study participants will be randomly selected to do the Active phase first and the Placebo phase second)				Ovulating Testing	ACTIVE E2 + P4				Ovulating Testing	PLACEBO patch and pills			1 Hour Debriefing Visit	
Order B (Half of study participants will be randomly selected to do the Placebo phase first and the Active phase second)				Ovulation Testing	PLACEBO patch and pills				Ovulating Testing	ACTIVE E2 + P4				
Laboratory Visits (90 minutes)					XXXXX					XXXXX				
Evening Surveys (3-5 minutes)		X	X	X	X		X	X	X	X		X		
Daily Phone Call (1 min per day)							X					X		
Using "BiAffect" App Keyboard		X	X	X	X		X	X	X	X		X		
Using Metricwire App		X	X	X	X		X	X	X	X		X		
Wearing Oura Ring		X	X	X	X		X	X	X	X		X		

SUB-STUDY TIMELINE	START	MONTH 1		MONTH 2				END	
	Enrollment Visit	Baseline Menstrual Cycle	OBSERVATIONAL MENSTRUAL CYCLE						
			Week 1	Week 2	Week 3	Week 4			
Ovulation Testing				X					
Laboratory Visits (60 mins)					XXXXXX				
Evening Surveys (3-5 mins)		X	X	X		X			
Using "BiAffect" App		X	X	X		X			

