Using Metricwire App		X	X	X		X			

Table 1b. substudy activities and timeline.

The proposed substudy characterizes 1) normative cycle-related variation in neuroactive steroids and mRNA expression, and 2) group-related differences (i.e., past-month SI vs HC) in trajectories of GABAAR subunit change across the cycle. 60 healthy controls (HC) with no SI will be recruited to gain a completer number of 40 for a two-month long observational substudy, in which five lab visits across one menstrual cycle (timed identically to mirror the observations across one medication phase of the experimental trial) will capture baseline molecular/genetic changes for between-group comparisons. The basic timeline for participation can be seen in table 1b.

The **double-blind crossover experimental design** is identical to that used during the PI's recently-completed trial (K99MH109667; Fig. 6). The TOP (red) panel shows natural perimenstrual hormone withdrawal in the placebo condition; the BOTTOM (black) panel shows prevention of hormone withdrawal in the active E2+P4 stabilization condition. THIS IS NOT A CLINICAL EFFICACY TRIAL, but a RCT design will probe the effect of hormone withdrawal (vs. stabilization) on proximal suicide risk and mediators. Participants will be randomized to condition order A (see Table 1 above; Active E2+P4, washout cycle, then Placebo) or condition order B (Placebo, washout cycle, then Active E2+P4). Investigational Drug Services will manage the double-blind. In each two-week condition, participants will wear a weekly patch (E2 or placebo) and take a daily pill (P4 or placebo). Because this manipulation simply delays natural E2+P4 changes⁹⁶, and given our previous finding of benefit¹², this manipulation is *not expected to pose greater risk than a normal menstrual cycle*.

Timing and Duration. Participants will receive the first seven-day transdermal E2 patch (or placebo patch) and begin daily oral P4 (or oral placebo) at a lab visit scheduled seven days after a positive urine ovulation test (+7 in Fig 6). This coincides with a time in the natural cycle when E2+P4 are already elevated. The weekly patch will be changed at the lab visit on day +14. The goal of this E2+P4 manipulation is to extend and maintain the mid-luteal phase hormone profile beyond the point in the cycle (i.e., around day +10) that would normally be associated with natural hormone withdrawal. Therefore, the active condition effectively prevents perimenstrual E2 and P4 withdrawal.

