We will also collect a urine sample and perform rapid urine toxicology screens for amphetamines, barbiturates, benzodiazepines, cocaine, opioids, cannabis, and methamphetamine on-site through the CRC nursing staff using Alere iCup 12-Panel Drug Test with temperature-sensitive strips. Positive tests will be used primarily for data quality assurance and covariate purposes. Individuals with positive test results will be allowed to continue the study provided that the participant demonstrates an ability to safely complete all study procedures. When there is any positive test that is not

accounted for by an existing prescription, the participant's test results will be reviewed with the study physician and PI at routine team meetings.

At all 10 laboratory assessments during active treatment with placebo or E2/P4, participants will provide blood (35ml at each visit) to be assayed for E2/P4, neuroactive steroids, and from which we will perform RNA gene expression assays, to evaluate the success of the hormone in achieving stable luteal phase levels of E2/P4/ALLO, as well as more stable gene expression markers of risk across various systems (neurosteroidogenic enzymes, GABA-A receptor subunits, and other mechanisms such as inflammatory cytokines). Blood will be collected as follows: (1) 30ml in red-top tubes (no additive), and (2) 5ml in PaxGene RNA tubes, at 2.5ml blood apiece. 30ml of blood (red-top tubes) will be centrifuged and plasma will be stored in cryovials, and the PaxGene tubes will be stored as well; when it is time for assay, samples will be transferred to [name] laboratory. Standard freezer-proof labels will indicate participant ID and study session. Transport from the CRC to [name] laboratory will be managed by Clinical Research Center staff. Samples will be analyzed in small batches with all of one participant's samples being run in the same batch. Following assay, any additional serum will be stored by [name]. Following assay, the PaxGene RNA blood samples will be destroyed.

Clinical assessments and laboratory sampling for HC participants (Aim 3 substudy).

Point-of-care pregnancy test, urine toxicology screen, and laboratory samples via blood draw are identical for HC participants as described above.

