In addition to the specific gene expression assays for neurosteroidogenic enzymes performed by [name], We will also perform “whole transcriptome shotgun sequencing” in each sample collected across both conditions, which measures the presence and quantity of RNA (related to the entire genome) in a given sample at a given moment. This will be used to test hypotheses regarding the effects of the manipulation on expression of genes coding for all neurosteroidogenic enzymes (not just those measured by [name] using qPCR), GABA-A receptor subunits, and inflammatory cytokines. These analyses will also be performed in-house at the University of Illinois.

Neuroactive steroids for HC participants (Aim 3 substudy).

Neuroactive steroids, mRNA, and genome sequence collection will be identical in the substudy as described above.

Smartphone-Based Assessments

Daily Symptoms Survey (3 minutes each evening throughout the 4-month Study). Each evening throughout the four months of the study, participants will complete the following self-report scales. First, the Daily Rating Form (DRF)⁵⁵, capturing hormone-related symptoms listed in the DSM-5^{118(p5)} (depression, hopelessness, worthlessness, anxiety, mood swings, rejection sensitivity, anger/irritability, interpersonal conflict, difficulty concentrating, lack of interest, insomnia, hypersomnia, overeating, lack of appetite, emotional overwhelm (hyperarousal), feeling out of control, fatigue, and physical discomfort). In addition to the DRF, participants will complete the Brief Agitation Measure (BAM)⁵⁴, a 3-item measure that taps into feelings of agitation (e.g., “I felt so stirred up inside that I wanted to scream”; hyperarousal) as well as dimensional ratings of the three highest-loading items from the Beck Hopelessness Scale¹⁷ (e.g., “The future seems dark to me”). This daily survey will provide an integrated rating of the patient’s symptoms across the entire day, consistent with methods used in seminal experiments of hormones and mood^{30,119,120}. Medication adherence, stressor exposure¹⁹, medication, drug, and alcohol use, sleep, pain, illness, and exercise will be recorded; any additional probing to clarify these online responses will be take place during the following day’s daily safety call.

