Testing Interactive Effects of Hopelessness and Arousal on Suicide Outcomes: Interactions among hopelessness and arousal will be examined as predictors of suicide outcomes and as mediators of the experimental effect. In order to test this, we examine day-to-day interactive effects of daily person-centered hopelessness (noted above) and daily person-centered arousal indices (noted above) predicting same-daily suicide outcomes (noted above). We predict that higher-than-usual hopelessness on a given day will predict greater same-day risk on suicide outcomes, but only when arousal is *also* higher than usual for that individual.

4. Evaluating Mediation Where Appropriate. Finally, each aim indicates that **mediation** will be explored as appropriate. Only when analyses indicate significant effects of the experiment on both the suicide outcome and any mediator, as well as significant associations between the person-centered variable (or interaction variable) and the suicide outcome, we will utilize methods provided by **Bauer, Preacher, and Gil (2006)** to construct a confidence interval for the level 1 indirect effect of experimental condition (condition X phase) on the suicide outcome via the mediator.

Testing for normative cyclical change in the HC group. Aim 3 seeks to characterize how gene expression for GABA_{AR} subunits varies across pre-specified menstrual cycle phase in response to hormonal change. In N=40 HC participants, we will run multilevel growth models to predict subunit gene expression (one model per gene) from specific cycle phase. We will test all pairwise comparisons between midluteal, perimenstrual, and midfollicular phases, controlling for ALLO level, to capture high P4 and ALLO states (midluteal), P4 and ALLO withdrawal (perimenstrual), and low P4 and ALLO (midfollicular).

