Testing for group differences between participants with past-month SI and HC. We hypothesize that clinical group moderates the effect of cycle phase on GABA_{AR} composition, such that the primary experimental group shows higher slope of midluteal-to-perimenstrual change in $\alpha 4$ and δ subunits, and lower $\gamma 2$ subunit replacement of δ subunit expression than the HC group. In one model of N=80 total participants, we will test the interaction of group and cycle phase on gene expression outcomes. We also hypothesize a correlation with symptoms, such that increases in $\alpha 4$ and δ subunit expression will be associated with increases in individuals with perimenstrual increases in SI. We also predict that even in the HC group, higher-than-average $\alpha 4$ or δ subunit expression will be associated with higher-than-average negative affect (e.g., depressed mood, anxiety, irritability, or perceived stress). We predict that higher $\gamma 2$ expression will be associated with lower negative affect and perceived stress. We will calculate a person-mean for each subunit's expression (mean level across 5 visits) and a deviation score at each visit (visit level minus person mean). We will test overall correlations (e.g., do participants with higher mean $\alpha 4$ expression have higher negative affect?) and interaction with cycle phase (e.g., does a perimenstrual increase in $\alpha 4$ expression *compared to person-mean* correlate with an increase in negative affect?). To further refine hypotheses, we will generate credible intervals using Bayesian methods in the context of multilevel modeling.

POWER ANALYSIS

80 completers achieves 80% power to detect conventionally small-to-medium sized effects that, in our estimation, are clinically meaningful (i.e., $f^2 = .10$, which would mean that the interaction of condition and phase had uniquely accounted for 10% of the variance in the outcome in the perimenstrual window; Selya et al., 2012, “*A Practical Guide to Calculating Cohen’s f^2 , a Measure of Local Effect Size*”). We posit that if hormone withdrawal (vs. experimental stabilization) does not account for at least 10% of the variance in the outcome during this critical risky window of the menstrual cycle, then this line of research, which involves significant participant burden, is not worth pursuing further.

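### The Aim 3 comparison of suicidal-ideation and control participants is set at N=80, which does not match the 90 + 40 completers planned, and no subset rule is given

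*Protocol*

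**What the plan says.** Protocol section 10.0, under the heading on group differences between SI and HC participants, gives the model: "In one model of N=80 total participants, we will test the interaction of group and cycle phase on gene expression outcomes". It does not say how the 80 divides between groups. Person-means are taken over five visits, and the condition those visits come from is not named. The preceding paragraph of section 10.0, on normative change in controls, fixes the size of one group: "In N=40 HC participants, we will run multilevel growth models to predict subunit gene expression (one model per gene) from specific cycle phase".

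The planned numbers are larger. Section 4.0 recruits "60 healthy controls (HC) (40 completers) with no lifetime history of SI". Section 3.0 states that "a new sample of 90 completers female outpatients with past-month SI will complete two counterbalanced conditions", and section 6.0 repeats the figure ("90 completer female outpatients with recent SI").

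Section 6.0 also describes the data that will exist. "At all 10 laboratory assessments during active treatment with placebo or E2/P4, participants will provide blood", and GABA-A receptor subunits are a named expression target. Sequencing is done "in each sample collected across both conditions", and collection in controls is stated to be identical. The control visits are "timed identically to mirror the observations across one medication phase of the experimental trial".

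The SAP covers Aims 1 and 2 only, so section 10.0 of the protocol is the only specification of this test.

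**The concern.** The hypothesis is a steeper midluteal-to-perimenstrual change in α4 and δ expression in the SI group than in controls. Its precision depends on the number of people in each group. A total of 80 cannot be made from 90 SI and 40 HC completers without leaving people out, and the plan gives no reason for leaving anyone out: no matching, no batching limit, no symptom criterion. The samples are drawn and sequenced in any case, so a smaller model saves no assay cost. An analyst following the text would either drop collected data or have to decide unaided what 80 refers to.

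**Working it through.** **The stated N.** No alpha, power, effect size or slope SD is given for Aim 3, so there is no calculation behind 80 to reproduce. The available sums are:
- SI completers (sections 3.0, 4.0, 6.0) plus HC completers (section 4.0): 90 + 40 = 130.
- With HC fixed at 40 (section 10.0), a total of 80 leaves 80 − 40 = 40 SI participants, so 90 − 40 = 50 are not used. The 40 + 40 split is an inference; only the total is printed.
- The nearby power statement in section 10.0 also says 80, but there it counts SI completers for the condition-by-phase test of Aims 1 and 2. Read that way, the Aim 3 total would be 80 + 40 = 120, again not 80.

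**Precision.** With per-person slope SD set to 1 in both groups, SE = √(1/n₁ + 1/n₂):
- 40 + 40: √(1/40 + 1/40) = .224
- 90 + 40: √(1/90 + 1/40) = .190
- Ratio .190/.224 = .85, a 15% smaller SE. The variance is 28% smaller, equivalent to 2/.190² ≈ 55 per group instead of 40.

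**Detectable difference**, 80% power, two-sided .05 (assumed): (1.960 + .842) × SE.
- 40 + 40: 2.802 × .2236 = .63 SD
- 90 + 40: 2.802 × .1900 = .53 SD

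Power at an assumed difference of .5 SD rises from 61% to 75%.

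**Sensitivity to the assumptions.**
- Alpha .05/3 (three subunits): .72 falls to .61 SD. Alpha .004: .83 falls to .71 SD.
- Unequal slope SDs, with r the SI-to-HC ratio: SE ratio = √(r²/90 + 1/40) / √(r²/40 + 1/40). This is .89 at r = .75 and .75 at r = 2, so the reduction in SE runs from 11% to 25%.
- Dilution: suppose only a fraction p of SI participants have the steeper slope and the rest match controls. Ignoring the extra spread this adds, the all-participant analysis has signal p·d/.190, against d/.224 for 40 participants who all have it. These are equal at p = .190/.224 = .85. Above that, using everyone is better; below it, a well-chosen 40 is better. In the preliminary data in section 2.0, 28 of 30 participants (93%) had their highest mean SI perimenstrually. That figure concerns ideation, not expression slopes, so it is only an indication.

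**The case against.** The strongest objection is that a subset may be intended. Section 3.0 frames Aim 3 around people with and without perimenstrual changes in affect and suicide risk, and places the hypothesis in a group that shows such increases. If so, adding every SI participant could dilute the contrast. This stands as a possibility. However, section 10.0 names the comparison group simply as the primary experimental group, and neither section gives a rule or a size.

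A second objection is that 80 may be a figure that was not updated: the protocol's power text uses 80 completers, the SAP 85, and the design 90. That is plausible, and it would make this an inconsistency rather than a decision to discard data. The correction to the text is the same.

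Third, section 2.0 calls the control substudy exploratory, and Aims 1 and 2 are unaffected. Both are true and limit the weight of the point.

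Two stronger readings are tempting. A reader might infer that hormone-treated cycles could be pooled into the SI slope and flatten it. The documents do not support this. A five-visit person-mean covers one cycle, the control visits mirror a single medication phase, and section 10.0 defines the perimenstrual phase as progesterone and allopregnanolone withdrawal, whereas the active condition is designed to prevent perimenstrual hormone withdrawal. Together these point to the placebo cycle, although the word is not attached to the comparison. A reader might also infer that 40 SI participants would be picked after expression results are known. Nothing in the documents describes such a choice.

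**Conclusion.** The concern holds as a mismatch in numbers with a moderate cost. N=80 does not fit the 90 SI and 40 HC completers whose RNA is planned, and no subset rule is stated. On the inferred 40 + 40 split, about 50 SI placebo cycles go unused. Including them reduces the SE of the slope difference by about 15% and the detectable difference from about .63 to .53 SD. These figures rest on two-sided .05, equal slope SDs, complete data and the same effect in every SI participant, none of which the documents state for Aim 3. The unnamed condition is a gap in wording whose likely meaning is clear, and no loss is attributed to it here.

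**What to change.** In Protocol section 10.0, replace the total of 80 with all HC participants and the placebo-condition visits of all SI participants, about 130 completers. State that SI person-means and visit deviations are taken over the five placebo-condition visits, which also settles the cycle being compared. If the Aim 3 wording in section 3.0 is meant to define a subset with perimenstrual increases, prespecify the rule and the expected size, and report that analysis alongside the all-participant one.

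The cost is protocol text only: no new visits, samples or sequencing. The downsides are small: unequal group sizes, which the multilevel model handles, and possible dilution if some SI participants have no perimenstrual increase, which the paired subset report would show.
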